8.4.3.3 Expectedness

The PI will be responsible for determining whether an AE is expected or unexpected. An AE will be considered unexpected if the nature, severity, or frequency of the event is not consistent with the risk information previously described for the study intervention.

8.4.4 Time Period and Frequency for Event Assessment and Follow-Up

The occurrence of an AE or serious adverse event (SAE) may come to the attention of study personnel during study visits and interviews of a study participant presenting for medical care, or upon review by a study monitor.

All AEs including local and systemic reactions not meeting the criteria for SAEs will be captured on the appropriate case report form (CRF). Information to be collected includes event description, time of onset, clinician's assessment of severity, relationship to study product (assessed only by those with the training and authority to make a diagnosis), and time of resolution/stabilization of the event. All AEs occurring during the study must be documented appropriately regardless of relationship. All AEs will be followed to adequate resolution. Any medical condition that is present at the time that the participant is screened will be considered as baseline and not reported as an AE. However, if the study participant's condition deteriorates at any time during the study, it will be recorded as an AE.

Changes in the severity of an AE will be documented to allow an assessment of the duration of the event at each level of severity to be performed. AEs characterized as intermittent require documentation of onset and duration of each episode.

Credentialed clinicians will record all reportable events with start dates occurring any time after informed consent is obtained until seven (for non-SAEs) or 30 days (for SAEs) after the last day of study participation. At each study visit, the investigator will inquire about the occurrence of AE/SAEs since the last visit. Events will be followed for outcome information until resolution or stabilization.

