1.2 SCHEMA

Abbreviated Title: COXes in MS

Version Date: 04/20/23

Visit 1
Time Point

Obtain informed consent. General medical history
and examination, and laboratory testing)

Visit 2-3
Time Point

Day hospital visits:
1 IV, pre-lab EKG
PET scan #1 at baseline with one tracer
PET scan #2 after blockade
Post-labs
Follow-up phone call

Visit 3-5
Time Point

Day hospital visits:
1 IV, pre-lab EKG
PET scan #1 at baseline with the other tracer
PET scan #2 after blockade
Post-labs
Follow-up phone call

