8.3 SAFETY AND OTHER ASSESSMENTS

- *Safety Monitoring of PET Scans.* Data for safety monitoring will be recorded at three timepoints: no more than three hours before injection, about the middle of the PET scan, and after the PET scan. Recorded data include: blood pressure, pulse, respiratory rate, and EKG (either 3- or 12-lead). The following laboratory tests will also be obtained, but only at two timepoints (before and after the PET scan): CBC, acute care panel (Na, K, Cl, CO₂, creatinine, glucose, urea nitrogen).
- *Pregnancy Tests.* For women of childbearing potential, urine pregnancy testing will be done within the 24 hours prior to any PET scan. If the pregnancy test is positive, PET will not be done, and the subject will be taken off the protocol.
- *Follow-up Procedures.* Subjects will be contacted one to three business days after each PET scan to determine whether they have had any untoward sequelae.

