8.4.5 Adverse Event Reporting

Non-SAEs will be reported to the ISM (annually), to the IRB at the time of Continuing Review and to the Sponsor at regular intervals per request.

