9.3.1 Evaluable for toxicity

No toxicity is expected from the radioligand; nevertheless, safety will be monitored as described in Section 8.3. Regarding the two blockers, participants will be asked if they have any discomfort or side effects after its administration and within one to three days after the PET scan via telephone.

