10.5 SAFETY OVERSIGHT

Monitoring for this study will be performed by the independent safety monitor (ISM) for this study, [name], who is with full clinical privileges at the NIH Clinical Center.

The PI will prepare a report on data and safety parameters for the ISM approximately every 12 months. The ISM will provide a written monitoring report to be submitted to the IRB at the time of continuing review.

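### Events are to be recorded to 7 and 30 days after last participation, but no contact is scheduled after a call 1–3 business days after the last scan, and no expedited route to the independent safety monitor is stated

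*Combined protocol and SAP*

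**What the plan says.** **Recording window.** Section 8.4.4 sets the period by onset date: from consent "until seven (for non-SAEs) or 30 days (for SAEs) after the last day of study participation". The last day of study participation is not defined. The synopsis gives a participant duration of 2–5 days, while the schedule of activities (1.3) allows the scans to be completed over two months.

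**Scheduled contact.** Section 8.3 says: "Subjects will be contacted one to three business days after each PET scan to determine whether they have had any untoward sequelae". Section 9.3.1, on the two blockers, says "within one to three days after the PET scan via telephone", without the word business. The schema (1.2) ends each scanning block with "Follow-up phone call" and lists nothing after it. Table 1 in section 1.3 has no row for the call and no contact at day 7 or day 30.

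**Other routes to an event.** Section 8.4.4 promises active enquiry at visits: "At each study visit, the investigator will inquire about the occurrence of AE/SAEs since the last visit". It also says that events may come to light "during study visits and interviews of a study participant presenting for medical care, or upon review by a study monitor".

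**Oversight.** On the independent safety monitor (ISM), section 8.4.5 says "Non-SAEs will be reported to the ISM (annually" and section 10.5 says "The PI will prepare a report on data and safety parameters for the ISM approximately every 12 months". Section 8.4.6 sends deaths to the sponsor within 24 hours of awareness, other SAEs within 48 hours, and all AEs quarterly by default. It names the Clinical Director/CEO and/or a designated medical monitor as recipients, with a copy to the regulatory support office. The ISM is not on that list.

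**The concern.** The plan promises recording for longer than anyone is scheduled to ask. No visit follows the last scan, so the enquiry at each visit cannot cover the time after it, and the safety labs in section 8.3 are taken only around the scan. The 24- and 48-hour clocks do not help, because they start when the study team becomes aware of an event. An SAE at, say, day 20 is recorded only if the participant volunteers it, presents for care in a way that reaches the team, or a monitor finds it.

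At stake is what a 30-day SAE record means. Section 2.3.1 lists serious reactions for both blockers and relies on monitoring of participants. With 16 participants, one missed event changes the safety description.

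The second issue is who learns of an SAE, and when. Section 10.5 gives monitoring of the study to the ISM, yet the expedited route in section 8.4.6 runs through the sponsor side. Section 10.9 states that the Clinical Director is also the IND sponsor. On the text, the ISM could first see an SAE in the next periodic report, after further participants have been dosed.

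**Working it through.** The plan gives no derived figure to reproduce. The check compares sections and does calendar arithmetic.

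**Inputs**
- Windows: 7 days (non-SAE) and 30 days (SAE), section 8.4.4.
- Last contact: 1–3 business days after the scan, section 8.3.
- Accrual 16 and study duration 36 months, synopsis.
- One ketoprofen and one celecoxib dose per participant who completes all scans, section 2.3.1.
- 11 participants wanted with complete scans; 30–40% expected not to complete, section 9.2.

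**Step 1: business days to calendar days.** For weekday scans, ignoring holidays, 1, 2 and 3 business days later are:

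| Scan day | Calendar days to the call |
|---|---|
| Monday | 1, 2, 3 |
| Tuesday | 1, 2, 3 |
| Wednesday | 1, 2, 5 |
| Thursday | 1, 4, 5 |
| Friday | 3, 4, 5 |

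The call therefore falls 1 to 5 calendar days after the scan.

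**Step 2: days after the last scheduled contact** = window − days to the call.

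*If participation ends on the day of the last scan:*
- SAE: 30 − 5 = 25 to 30 − 1 = 29 days (25/30 = 83% to 29/30 = 97%).
- Non-SAE: 7 − 5 = 2 to 7 − 1 = 6 days (2/7 = 29% to 6/7 = 86%).
- With section 9.3.1's plain days (1–3): 27 to 29 and 4 to 6 days, inside the same ranges.

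*If participation ends at the call:* all 30 and all 7 days follow it.

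**Step 3: which scans this affects.** After an earlier scan the next visit asks about events since the previous one, so the gap follows the final scan only.

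**Step 4: exposure between yearly ISM reports**, assuming even accrual over 36 months.
- Participants: 16 × 12/36 = 5.3.
- Blocker doses if all 16 complete: 5.3 × 2 = 10.7.
- Blocker doses counting only 11 completers: 11 × 12/36 × 2 = 7.3. Participants who stop early may still have had one dose, so the true figure lies between the two.
- Accrual concentrated in a shorter period would put more participants between reports.

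**The case against.** **The sections do not contradict each other.** A reader might infer that 8.3 and 8.4.4 conflict. They do not. One says which events must be recorded, the other when staff call, and a recording window may run beyond the last contact. This stands. The point is that ascertainment becomes passive, not that the text is inconsistent.

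**Other reviewers see SAEs quickly.** A reader might infer that the ISM is the only independent reviewer, or that nobody able to act learns of an SAE for a year. The documents say otherwise. Sections 8.4.2 and 8.5.2 send AE evaluations and unanticipated problems to the IRB under Policy 801. Section 8.4.6 informs the sponsor side within 24 or 48 hours and the FDA within 7 or 15 days where an event qualifies. Section 10.2 allows suspension for unacceptable risk. This stands too: any delay concerns the ISM alone.

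**The yearly limit on SAEs is not stated.** The annual schedule in section 8.4.5 covers non-SAEs only. For SAEs the plan is silent on an expedited ISM route, and silence is not a prohibition. Policy 801 and the monitoring plan mentioned in section 10.6 are not available here and may contain one. That is a fair limit, but the protocol itself still does not state the route.

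**Days are not risk.** The 83–97% counts calendar days. Exposure is to single doses, section 8.2.1 waits at least two days for a blocker's effect to resolve, and section 2.3.1 rates serious reactions as unlikely. Late related events may be rare, so the percentage must not be read as a share of events missed. It remains true that the plan itself chose 30 days, for SAEs whether or not related.

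**Conclusion.** The point holds as a cheap improvement to safety conduct. After the final scan no scheduled contact reaches the end of either recording window: capture is passive for 25–29 of 30 SAE days and 2–6 of 7 non-SAE days, or for all of both, depending on an undefined term. Separately, the protocol states no expedited route for SAEs to the ISM. About 5 participants and roughly 7–11 blocker doses would fall between yearly reports.

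These figures assume weekday scans without holidays, even accrual over 36 months, and completion between 11 and all 16 participants.

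It would be wrong to infer that the trial's result is at risk. Section 9.4.4 says that safety measurements are not analysed statistically, and the primary comparison of baseline and blocked scans is untouched. The effect is confined to completeness of safety ascertainment and timeliness of independent oversight.

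**What to change.** - **8.4.4:** define the last day of study participation, so that both windows have a fixed start.
- **8.3, 9.3.1 and Table 1:** add one scripted telephone call at the end of the 30-day SAE window, asking about any event since the last contact, with onset dates. The dates also show which non-serious events began within 7 days.
- **8.3 and 9.3.1:** use the same unit, days or business days, for the early call, and show that call in Table 1.
- **8.4.6 and 10.5:** copy the ISM on each SAE report when it goes to the sponsor.

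Do not resolve the mismatch by shortening the recording windows: that would remove the duty to record late events that do become known.

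The cost is up to 16 short calls over the study, one added report recipient and an amendment to the wording. No visit or test is added.

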8.4.5 Adverse Event Reporting

Non-SAEs will be reported to the ISM (annually), to the IRB at the time of Continuing Review and to the Sponsor at regular intervals per request.

8.4.6 Serious Adverse Event Reporting

It is both the Principal Investigator's (PI) and the Sponsor's responsibility to ensure the safety of those on the clinical trial. The PI is responsible for tracking adverse events during the study and providing adverse events lists to the Sponsor at regular intervals per request. These may be requested quarterly and will be requested no less than once a year at the time of IND annual report to the FDA. ALL AEs that are collected, as determined by the written protocol, should be tracked in the ORSC RSS' template AE Tracker or similar document. If the sponsor determines that adverse events are occurring more frequently or more severely than the written protocol had expected and/or anticipated, this should be submitted in an IND Safety Report, as described below. In addition, the PI is responsible for updating the Sponsor about known risks from the drug, as discovered from literature searches or other means. In addition, the PI is responsible for updating the Sponsor about known risks from the drug, as discovered from literature searches or other means.

In accordance with the requirements of 21 CFR 312.32, the PI or designee will report all SAEs, whether or not these are considered related to the investigational drug or study intervention, that occur throughout the study to the Sponsor, including those events listed in the protocol or Investigator's Brochure as anticipated to occur, as follows:

Deaths: within 24 hours of the investigator's* awareness

All other SAEs: within 48 hours of the investigator's awareness

All AEs will be sent to the Sponsor quarterly, unless requested more or less frequently, for submission to the FDA in the IND Annual Report.

*“Investigator's awareness” includes awareness by anyone on the study team.

The PI will immediately report all deaths and SAEs to the Sponsor by disclosing all event-related information in a completed MedWatch Form 3500A. This form should include the IND number, protocol number, PI name, and an assessment on the reasonable possibility of a relationship between the event and the study drug or intervention. **MRNs should NOT be included on this form.** The completed MedWatch Form 3500A will be sent **ENCRYPTED** to the Clinical Director/CEO and/or designated medical monitor with a copy to the NIH Office of Research Support & Compliance (ORSC) Regulatory Support Section.

The Clinical Director/CEO and/or designated medical monitor will be responsible for determining whether the event is reportable to the FDA as an IND Safety Report if it is a serious, unexpected, and suspected adverse reaction (SUSAR). If the sponsor determines the SAE meets the criteria of a SUSAR, the ORSC will submit an Initial IND Safety Report to the FDA no later than 15 calendar days after the PI's notification of the event to the Sponsor. Deaths or life-threatening events will be reported to the FDA no later than 7 calendar days after the PI's notification of the event to the Sponsor. The Sponsor will submit any relevant additional information in a Follow-up IND Safety Report no later than 15 calendar days after receiving the information. All SAEs will be monitored until satisfactory resolution. All AEs and SAEs will be documented on appropriate study records.

8.4.7 Events of Special Interest

None.

8.4.8 Reporting of Pregnancy

Subjects will be excluded if they are or may become pregnant.

8.5 UNANTICIPATED PROBLEMS

8.5.1 Definition of Unanticipated Problems (UP)

Any incident, experience, or outcome that meets all of the following criteria:

- Unexpected in terms of nature, severity, or frequency given (a) the research procedures that are described in the protocol-related documents, such as the Institutional Review Board (IRB)-approved research protocol and informed consent document; and (b) the characteristics of the participant population being studied; and
- Related or possibly related to participation in the research (“possibly related” means there is a reasonable possibility that the incident, experience, or outcome may have been caused by the procedures involved in the research); and
- Suggests that the research places participants or others (which many include research staff, family members, or other individuals not directly participating in the research) at a greater risk of harm (including physical, psychological, economic, or social harm) than was previously known or expected.

8.5.2 Unanticipated Problem Reporting

The investigator will report unanticipated problems (UPs) to the NIH Institutional Review Board (IRB) as per Policy 801.

8.5.3 NIH Intramural IRB Reporting of IND Safety Reports

Only IND Safety Reports that meet the definition of an unanticipated problem will need to be reported to the NIH Intramural IRB.

9 STATISTICAL CONSIDERATIONS

9.1 STATISTICAL HYPOTHESIS

- Primary Endpoint: We hypothesize that administration of ketoprofen or celecoxib will reduce COX-1 or COX-2 levels (measured as SUVR between a lesion and a reference region such as the contralateral mirror image of the lesion) in MS lesions. Please note that detectable or specific binding is defined as that which can be displaced by a COX selective inhibitor. Thus, the primary objective “detectable binding” will be assessed with the primary endpoint “displaceable binding.”
- Secondary Endpoint: 1) We hypothesize that more active MS lesions will have higher levels of COX-1 and COX-2 specific binding than less active ones, and that MS lesions will have higher binding than normal white matter. Active lesions will be identified as those that show contrast enhancement with administration of gadolinium. Chronic-active lesions will be identified as those who have a paramagnetic outer rim identified on ME-GRE images that have been processed for quantitative susceptibility maps (QSM). Inactive lesions will be white matter

lesions that do not meet criteria for active or chronic-active. Normal appearing white matter will be all white matter minus lesioned white matter. 2) We hypothesize that the expressions of COX-1 and COX-2 are correlated within the same individuals.

9.2 SAMPLE SIZE DETERMINATION

Using novel radioligands, this pilot study will attempt to measure the density of COX-1 and COX-2. When the standard deviation and the effect size are unknown, the resource equation method provides an alternative to the power analysis for calculating sample size [24-27]. This method is based on the law of diminishing returns and is normally used in animal experiments to minimize the number of animals committed to an exploratory study. The minimum and maximum sample sizes calculated using the equation are:

$$\text{minimum } n = 10/k + 1$$

$$\text{maximum } n = 20/k + 1$$

where k = number of groups and n = number of samples per group

For example, if there are two groups to compare (e.g., baseline vs blocked studies in the same participants), the minimum $n = 10/2 + 1 = 6$ and the maximum $n = 20/2 + 1 = 11$.

Expressed in other terms, using fewer than six participants per group would have little value because of a high rate of false negatives. On the other hand, using more than 11 participants per group would have diminishing return of true positives.

Following this statistical approach, we request to scan 11 participants per group. Because of the failure rate for completing all scans is 30-40%, we request permission to accrue 16 participants per group.

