5 STUDY POPULATION

Patients with MS will be recruited by referral from the PI at UMB, with subjects being those who are currently enrolled under UMB protocol HP-00079860 and who have signed a clause in the UMB consent document allowing contact for future research.

Healthy subjects won't be needed for this study because MS subjects scanned at baseline will be their own controls for the scans after blockade.

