9.3 POPULATIONS FOR ANALYSES

Using a within-subject comparison, the baseline scan of each MS participant will be compared to that after blockade

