9.4 STATISTICAL ANALYSES

9.4.1 General Approach

Two-tailed paired: t-tests will be used to assess whether there are statistically significant differences between PET scans at baseline and after blockade.

ANOVA will be used to assess whether COX-1 and COX-2 binding differs in active, chronic-active, and inactive lesions, and normal appearing white matter.

Correlation analyses will be used to correlate the uptake of COX-1 and COX-2 in the same lesions of the same subjects.

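### Section 9.2: accruing 16 yields 11 expected all-scan completers only up to 31.25% failure, not across the stated 30-40%, and the formula giving 11 as a maximum is for independent groups, not the planned paired test

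*Combined protocol and SAP*

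**What the plan says.** Section 9.2 treats the effect size and standard deviation as unknown and uses the resource equation in place of a power calculation: minimum n = 10/k + 1 and maximum n = 20/k + 1, where k is the number of groups and n the number per group. It takes k = 2, with the wording "if there are two groups to compare (e.g., baseline vs blocked studies in the same participants), the minimum" being 6 and the maximum 11. It interprets the limits by saying that "using fewer than six participants per group would have little value because of a high rate of false negatives" and that "using more than 11 participants per group would have diminishing return of true positives". On this basis, "we request to scan 11 participants per group". The accrual figure follows: "Because of the failure rate for completing all scans is 30-40%, we request permission to accrue 16 participants per group". No calculation linking 11 to 16 is shown.

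Elsewhere the design is one cohort measured twice. Section 5 says that "MS subjects scanned at baseline will be their own controls for the scans after blockade". Section 9.3 says: "Using a within-subject comparison, the baseline scan of each MS participant will be compared to that after blockade". Section 9.4.1 specifies two-tailed paired tests: "t-tests will be used to assess whether there are statistically significant differences between PET scans at baseline and after blockade". The synopsis (1.1) gives a total of 16 participants, and the schedule of activities (1.3) gives four PET scans each, two per radioligand.

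**The concern.** There are two separate problems in the one paragraph.

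- **Accrual.** The 16 is presented as the allowance for 30-40% failure, but it matches only the low end of that range. The IRB is told that the target is protected against losses which the number does not cover.
- **Formula.** The equation counts baseline and blocked scans as two separate groups. In the planned analysis they are two measurements on each person, and the paired test has fewer error degrees of freedom. The maximum of 11 and the minimum of six are then presented as properties of a test that the formula does not describe. A reader could conclude that data from a 12th to 16th completer add little, or that six would be enough.

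There is also a point of clarity. The failure rate refers to completing all scans, while each tracer's primary test needs only that tracer's two scans. The plan does not say explicitly whether a participant with one complete pair is analysed.

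**Working it through.** **Inputs, all from section 9.2 unless noted:** target 11; accrual 16; failure to complete all scans 30-40%; k = 2; limits 10/k + 1 and 20/k + 1; paired t-test (9.4.1); four scans, two per tracer (1.3). The 35% midpoint is added for illustration.

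**1. The plan's own figures.** 10/2 + 1 = 6 and 20/2 + 1 = 11, as printed. Accrual at 30%: 11/0.70 = 15.7, rounded up to 16. So 16 reproduces at the low end.

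**2. Accrual across the stated range.** Expected completers = 16 × (1 − failure rate). Accrual needed = 11/(1 − failure rate), rounded up.

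| Failure rate | Expected completers from 16 | Shortfall against 11 | Accrual needed for 11 |
|---|---|---|---|
| 30% | 16 × 0.70 = 11.2 | 0 | 11/0.70 = 15.7 → 16 |
| 35% | 16 × 0.65 = 10.4 | 0.6 | 11/0.65 = 16.9 → 17 |
| 40% | 16 × 0.60 = 9.6 | 1.4 | 11/0.60 = 18.3 → 19 |

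Break-even is 1 − 11/16 = 31.25%, so 16 meets the target over the lowest 1.25 of the 10 percentage points, one eighth of the range. Multiplying instead of dividing gives 11 × 1.40 = 15.4, rounded up to 16. That may be where the 40% end came from, but the plan does not say.

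**3. Chance of reaching each number**, assuming participants drop out independently (binomial, 16 trials), at 30 / 35 / 40% failure:

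- at least 11 complete all scans: 66% / 49% / 33%
- at least 6, the plan's stated minimum: 99.8% / 99.4% / 98.1%

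**4. Pairs per tracer.** Let C be the expected all-scan completers. If every failure loses both pairs, each tracer has C pairs. If every failure loses only one pair, the average over the two tracers is (16 + C)/2. The ranges are 11.2-13.6, 10.4-13.2 and 9.6-12.8 at 30, 35 and 40%. The documents give no per-tracer failure rate to narrow them.

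**5. What the formula measures.** n = E/k + 1 rearranges to k(n − 1) = E, the error degrees of freedom of k independent groups. With k = 2: 2 × (6 − 1) = 10 and 2 × (11 − 1) = 20.

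For a paired t-test with one value per participant, the error degrees of freedom are n − 1: 5 at n = 6 and 10 at n = 11. One value per participant is an assumption, because the plan does not say how several lesions are combined. If the same 10-20 range is carried over to the paired test (an inference, since section 9.2 states no degrees-of-freedom criterion), n − 1 = 10 to 20 gives n = 11 to 21. Eleven lies in both windows: at the top of one and at the bottom of the other.

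**6. Scale only.** Assuming two-sided 5% alpha and 80% power (neither is in the plan), the detectable paired difference in SD units of the differences is 0.94 at n = 11, 1.00 at n = 10 and 1.07 at n = 9. With an assumed standardised difference of 0.8, power is 67% at n = 11 and 85% at n = 16, so gains beyond 11 need not be negligible.

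**The case against.** The strongest reply is that the primary tests may not fall short at all. Eleven can be read as 11 baseline/blocked pairs per comparison, and an all-scan failure rate is then a conservative basis for inflation. Section 9.3 does not restrict the test to all-scan completers, and even at 40% failure the range of 9.6-12.8 pairs per tracer includes 11. This stands as far as it goes: a shortfall in the primary tests is not shown. But the plan's own inflation step ties 11 to the all-scan rate, and on that basis 16 does not deliver 11. The correlation between COX-1 and COX-2 uptake needs both tracers, so partial completers do not help it.

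It can also be said that this is a pilot, that 9.6 is still well above the stated minimum of six, and that 11 remains admissible on either reading of the formula. All of that is true and limits the consequence, though six comes from the same ill-fitting formula. The 11-21 window rests on two assumptions and should not be printed as a requirement. The algebra in step 5 does not depend on it: the printed equation describes independent groups, and the planned test is paired.

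Finally, per-group wording for a single cohort is loose but harmless, since 16 agrees with the synopsis.

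**Conclusion.** Both points hold. As written, 16 accrued gives the target of 11 expected all-scan completers only for failure rates up to 31.25%, and the expected shortfall reaches 1.4 at the 40% end. That part uses only figures printed in section 9.2; the probabilities additionally assume independent dropout. The 6 to 11 window comes from an independent-groups formula, so it does not support an upper cut-off of 11 or a minimum of six for the paired test. It does not show that 11 is too few. The practical effect is modest and no change in design follows, but the justification given to the IRB should agree with its own numbers and its own test. It should be corrected.

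**What to change.** Reword section 9.2 without enrolling more, for example:

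> One cohort of up to 16 participants will be scanned at baseline and after blockade, with a target of 11 completing all four scans. The resource equation as written gives the error degrees of freedom of independent groups; the planned paired test has n − 1 with one value per participant, so 11 is a target and not an upper limit. At 30-40% failure to complete all scans, 16 participants give about 11.2 to 9.6 all-scan completers; 16 covers failure up to 31.25%. The possible shortfall is accepted for a pilot study.

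Delete the sentence about diminishing return above 11, and stop presenting six as a minimum derived for this test. Do not put 11 in its place as a threshold below which the study has little value. If a reason for 11 is wanted, it can be that 11 participants leave 10 error degrees of freedom in the paired test, on the same one-value-per-participant assumption. Remove the per-group wording (editorial).

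Add to 9.3 or 9.4.1:

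> Each tracer's paired test uses every participant with both scans of that tracer.

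No power or detectable-difference figures need to be added. The cost is a few sentences in an amendment, which needs IRB review under the Statement of Compliance. There are no extra participants or scans and no change of test. The only downside is that the stated expected number of completers becomes slightly less favourable than the 11 now implied.
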